2.2.2 Open-label Treatment Period (Extension Phase)

This SAP addresses only analyses for the double-blind phase of the study; however, an open-label extension phase will follow the double-blind phase, and the analyses for the extension phase will be covered in a separate SAP.

2.3 Study Population

Subjects to be included are male and female hemodialysis subjects aged 18 years of age or older with end-stage renal disease (ESRD) who have been on hemodialysis 3 times per week for at least 3 months prior to start of screening, have moderate-to-severe pruritus (mean baseline Worst Itching Intensity NRS score >4 with at least 4 worksheets completed in the run-in period), and meet additional eligibility criteria. A full list of the inclusion and exclusion criteria can be found in the CR845 protocol (v1.0 21DEC2017).

2.4 Treatment Regimens

Subjects will be administered CR845 0.5 mcg/kg or placebo as a single IV bolus 3 times a week after each dialysis session for 12 weeks during the Double-blind Treatment Period.

No study drug will be administered during the Discontinuation Period.

During the Open-label Treatment Period, subjects will be administered CR845 0.5 mcg/kg as a single IV bolus 3 times a week after each dialysis session for up to 52 weeks.

2.5 Treatment Group Assignments or Randomization

Before the start of the study, computer-generated randomization schedules will be prepared. Randomization will be performed using an interactive voice or web response system. Subjects will be randomized in a 1:1 ratio to receive either CR845 0.5 mcg/kg IV or matching placebo IV during the Double-blind Treatment Period. Subjects will be stratified according to use and no use of concomitant medications to treat itching during

the week prior to randomization (Run-in Period), as well as the presence or absence of specific medical conditions, for a total of 4 strata.

All eligible subjects providing consent for participation in the Open-label Treatment Period will receive CR845 at a dose of 0.5 mcg/kg starting on Day 1 of the Open-label Treatment Period.

2.6 Sample Size Determination

The planned sample size for this study is 350 (175 per treatment group) male and female hemodialysis subjects with chronic moderate-to-severe pruritus (mean baseline 24-hour Worst Itching Intensity NRS score >4), randomized at approximately 80 clinical sites. The sample size may be increased to 500 subjects (250 per treatment group) based on the results of a planned unblinded interim assessment conducted when approximately 50% of the planned 350 first subjects have been randomized and have either completed the 12-week Double-blind Treatment Period or have discontinued from treatment early. The planned interim assessment will be conducted by an Independent Data Monitoring Committee (IDMC). Details related to the sample size re-estimation are included in Section [11](#).

The sample size calculation is based on results of a completed phase 2 double-blind, placebo-controlled study (CR845-CLIN2101) of CR845 in hemodialysis subjects with ESRD who had moderate-to-severe pruritus. In this study, 30% of subjects randomized to the placebo group reported ≥ 3 -point improvement from baseline with respect to the 24-hour Worst Itching Intensity NRS at the end of treatment (Week 8). The proportion of subjects who received CR845 and reported a similar improvement in itch scores ranged from approximately 60% to 45% (i.e., 30% to 15% difference from placebo), depending on the dose of active study drug (0.5 mcg/kg, 1.0 mcg/kg, 1.5 mcg/kg).

Given a sample size of 350 subjects (175 per treatment group) and assuming a true response rate of 30% for the placebo group and a true response rate of 50% for the CR845 group (defining response as an improvement from baseline ≥ 3 points with respect to the Worst Itching Intensity NRS at Week 12), a 2-sided continuity corrected Chi-square will have 96% power to detect a treatment difference. The power of this test statistic would be $\geq 84\%$ for differences from placebo as low as 0.16 ([Table 1](#)).

Table 1 Power as a Function of Odds Ratio (N = 175 per arm)

Placebo Response	0.30	0.30	0.30	0.30
CR845 Response	0.50	0.48	0.46	0.45
Odds Ratio	2.333	2.154	1.988	1.909
Power^a	96%	92%	84%	79%

a. Power for a 2-sided Chi-square continuity-corrected test and a 5% Type 1 error.

Based on results of a planned interim assessment, the sample size may be increased up to 500 subjects (250 per treatment group). Given this maximum sample size, and assuming a true response rate of 30% in the placebo group, a 2-sided continuity corrected

Chi-square would have approximately 90% power to detect a treatment difference when the CR845 response rate is 45% (a 15% difference from placebo) (Table 2).

Table 2 Sample Size as a Function of Odds Ratio (90% Power)

Placebo Response	0.30	0.30	0.30	0.30	0.30
CR845 Response	0.50	0.48	0.46	0.45	0.44
Odds Ratio	2.333	2.154	1.988	1.909	1.833
Sample Size^a	134	164	204	230	262

a. Sample size for a 2-sided Chi-square continuity-corrected test and a 5% Type 1 error.

3. GENERAL ANALYSIS AND REPORTING CONVENTIONS

This section discusses general policies to be employed in the analysis and reporting of the data from the study. Departures from these general policies will be described, if applicable, in the appropriate sections of this SAP. When this situation occurs, the rules set forth in the specific section take precedence over the general policies.

For categorical variables, summary statistics will consist of the number and percentage of subjects in each category. All percentages will be rounded to one decimal point. The number and percentage of subjects will always be presented in the form XX (XX.X%) where the percentage is in parentheses. To ensure completeness, all summaries for categorical and discrete variables will include all categories, even if none of the subjects had a response in a particular category. Denominators for each analysis will be based on the population of interest (e.g., safety population; subjects with non-missing data).

For continuous variables, summary statistics will consist of the number of subjects with data, mean, median, standard deviation, minimum, and maximum values. The summary statistic n will be the number of subjects with non-missing values. All means and medians will be reported to one more significant digit than the values being analyzed. Standard errors and standard deviations will be reported to two more significant digits than the values being analyzed. The minimum and maximum will be reported to the same number of significant digits as the values being analyzed.

For tests of hypothesis of treatment group differences, the associated p-value will be reported. All p-values will be rounded to three decimal places; p-values that round to 0.000 will be presented as “<0.001”. P-values are descriptive for outcomes and analyses not included in the multiplicity algorithm.

In general, the baseline value will be considered the last non-missing measurement observed prior to the first dose of study treatment; the NRS will use the mean of the Run-in Period. The opiate withdrawal scales will use the Day 85 assessment as baseline.

For efficacy, subjects will be analyzed according to randomized treatment. For safety analyses, subjects will be analyzed according to the actual treatment received. Data from all sites will be pooled for the purpose of analysis. For analyses involving randomization strata, subjects will be analyzed according to actual strata recorded. It is possible that some values will be updated for the strata variables between the time of the interim analysis and the final database lock; for the final analyses, the values from the locked database will be used.

Data will be listed by treatment and subject. In general, listings will be sorted in the order that columns are displayed, starting with the first column on the left (treatment). Subject listings of data will be presented for all randomized subjects unless specified otherwise.

Unless otherwise specified, summaries will include the following treatment groups:

- CR845 0.5 mcg/kg
- Placebo

SAS statistical software, version 9.4 or higher, will be used for all analyses.

3.1 Assessment Time Windows

For the primary analysis variable, assessment time windows are not needed since the NRS Itch Intensity Assessments Log collects the individual scores and average Worst Itching Intensity NRS score for screening and each post-baseline visit week.

Assessments collected by study week that are collected at early termination visits and unscheduled visits will be assigned to a planned visit window, if the early termination or unscheduled visit day falls between +/- 3 days of the planned visit. Exceptions to this assignment include the double-blind Week 12 visit, which will use a window of +1/-3, and any discontinuation period visit, in which only exact matches to the planned visit day will be mapped. Should more than one measurement fall within a visit window, priority is given first to the measurement with a non-missing value in the following order: first, the scheduled assessment; second, an early termination visit; and next, the unscheduled assessment closest to the planned day. In the case that two unscheduled visits are equidistant, the latest will be used. This rule will be applied both to efficacy and safety endpoints.

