Record dose of ESA and IV iron	X		Record on an ongoing basis						X		
Record number of missed dialysis visits and reason(s)			Record on an ongoing basis								
IV administration of study drug			Record on an ongoing basis								
Inflammatory biomarker samples ^o			X						X		
Adverse event monitoring	X	X	Record on an ongoing basis						X	X	
Concomitant medications (including antipruritic medications) ^p			X	Record on an ongoing basis						X	X
Structured Safety Evaluation ^f		X		X			X			X	

DP = Discontinuation Period; ESA = erythropoiesis-stimulating agent; F = Friday; IV = intravenous; M = Monday; NRS = numerical rating scale; OOWS = Objective Opiate Withdrawal Scale; PRO = patient-reported outcome; Sa = Saturday; ShOWS = Short Opiate Withdrawal Scale; Th = Thursday; Tu = Tuesday; W = Wednesday

-
- a. Each visit during the Double-blind Treatment Period will coincide with the patient's normal dialysis treatments.
 - b. The End-of-Treatment Visit in the Double-blind Phase will be the first dialysis visit following the last dose of study drug (ie, first dialysis on Week 13 [Day 85]), which also corresponds to Day 1 of the Discontinuation Period (DP Day 1).
 - c. Medical history will be updated on Day 1 with any changes since the Screening Visit, and inclusion/exclusion criteria will be confirmed prior to randomization. Antipruritic medication will be updated at each dialysis visit during the Run-in Period.
 - d. Electrocardiogram must be performed prior to the start of dialysis at screening, Day 85 (End of Treatment), or at Early Termination visit.
 - e. Pre-dialysis vital signs, including body temperature, heart rate, and blood pressure, will be recorded on Days 1, 15, 29, 43, 57, 71 and 85 (End of Treatment), or at Early Termination visit only when the patient is in a sitting or semi-recumbent position. Heart rate will be measured at each dialysis; if heart rate is clinically significant and outside the prespecified visits per Schedule of Events, the heart rate will be recorded on the relevant CRF page.
 - f. Pre-dialysis vital signs, including body temperature, heart rate, and blood pressure, will be recorded at each dialysis visit during the Discontinuation Period. Heart rate will be measured at each dialysis.
 - g. Blood samples for clinical laboratory evaluation will be taken at screening, and on Days 1 and 85 (End of Treatment), or at Early Termination visit only.

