- For each questionnaire, the total score at each visit will be computed from the domain scores for each imputed dataset.
- The ANCOVA analysis described above will be implemented for each imputed dataset.
- Results of the ANCOVA on the multiply imputed data sets will be summarized by the SAS MIANALYZE procedure.

Since the observed change from baseline at Week 12 among the non-imputed data will be reported with the MMRM analyses described below, only the LS means, standard errors, 95% CIs, and differences between treatment groups reported with LS means, standard errors, and 95% CIs from the ANCOVA on the imputed data will be reported. The analysis will be completed for both the ITT and PP Populations.

Additionally, the 5-D Itch Scale and the Skindex-10 Scale scores will be analyzed using a mixed effects model with repeated measures (MMRM). The model will contain treatment, week, and treatment-by-week interaction as fixed effects, and baseline score and the randomization stratification variables as covariates. The baseline 5-D total score and the Skindex-10 total score will be defined as the value collected on Day 1, prior to randomization. Repeated measures will include values assigned at the end of Weeks 4, 8, 10, and 12 (end of treatment); see Section [3.1](#) for visit windowing.

It is important to note that, in HD subjects, the study drug administered during the last dialysis of a particular week is not cleared until the first dialysis of the next week. Therefore, measurements that would reflect treatment effect at the end of a specific week (e.g., Week 4) and labelled “end of Week xx” will actually be collected during the first day of the next week (e.g., Week 5).

An unstructured covariance matrix will be used to model the within-subject errors. Should the model fail to converge, a compound symmetric covariance matrix will be used instead. The Kenward-Roger approximation will be used to estimate the denominator degrees of freedom. Missing scores will not be imputed. Assuming that the data are

MAR, the estimates of the treatment differences calculated from the MMRM described above are unbiased.

Standard descriptive statistics will be reported for each time point on the values and changes from baseline along with the least squares (LS) means, standard errors, 95% CIs and differences between treatment groups reported with LS means, standard errors, and 95% CIs.

Worst Itching Intensity ≥ 4 -Point Improvement

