9.5 Vital Signs, and ECG

9.5.1 Vital Signs

Summary tables for vital signs will include descriptive statistics (number of subjects, mean, standard deviation, median, minimum, and maximum) for baseline and each post-baseline assessment. Descriptive statistics will be calculated on both the actual values and the change from baseline. Baseline is defined as the last measurement taken on or prior to the first day of dosing. Note that the Day 1 assessment can be included in the evaluation of baseline given that the assessment is performed prior to dosing.

All double-blind vital sign summaries will include the subjects in the Double-blind Safety Population or Double-blind Discontinuation Safety Population who have at least 1 post-baseline assessment (for criteria based on post-baseline assessments) and with both a baseline and at least 1 post-baseline assessment (for criteria evaluating changes from baseline).

Clinically notable vital signs will be identified based on the criteria below. For each vital sign parameter, the number and percentage of subjects with at least 1 notable value will be tabulated by week and overall for the Double-blind Treatment Period and Discontinuation Period separately.

Vital Sign Parameter	Value
Systolic blood pressure	≥180 mm Hg
	≤90 mm Hg
Diastolic blood pressure	≥100 mm Hg
	≤60 mm Hg
Heart rate	>130 bpm
	<55 bpm

bpm = beats per minute

All vital signs will be listed in by-subject listings, including visit and collection date/time, and will be sorted by subject identifier and date/time of assessment.

9.5.2 12-Lead ECGs

Standard 12-lead ECG readings with the subject in a supine position will be performed. Electrocardiogram results include an overall interpretation of “normal,” “abnormal but not clinically significant,” or “abnormal and clinically significant.” These results will be tabulated by treatment group and overall at each time point. Electrocardiogram values will also be listed by subject.

Clinically significant abnormalities at screening will be recorded as medical history. Clinically significant abnormalities or worsening of ECG findings observed after the first dose of study drug should be reported as adverse events.

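### The SAP visit windows leave nearly all Early Termination labs and ECGs without a post-baseline time point, and the SAP does not say whether off-schedule heart rates count as notable values overall

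*SAP*

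**What the plan says.** **The mapping rule.** SAP 3.1 places an ET or unscheduled assessment at a planned visit "if the early termination or unscheduled visit day falls between +/- 3 days of the planned visit". It adds: "Exceptions to this assignment include the double-blind Week 12 visit, which will use a window of +1/-3". If several values compete for one window, the non-missing value is taken in this order: "first, the scheduled assessment; second, an early termination visit; and next, the unscheduled assessment closest to the planned day". On scope it says: "This rule will be applied both to efficacy and safety endpoints". SAP Section 3 lets a specific section override a general convention, but SAP 9.4, 9.5.1 and 9.5.2 contain no rule for ET values.

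**Labs and ECGs.** Protocol 6.5.1, Table 2 footnote g, has blood samples taken at screening and "on Days 1 and 85 (End of Treatment), or at Early Termination visit only". Footnote d schedules ECGs at screening and at Day 85 or ET. Protocol 6.3.1 puts the ET visit at the first dialysis after the last dose or, failing that, as soon as feasible. SAP 9.4 summarises lab values and changes by time point. SAP 9.5.2 tabulates the ECG interpretation by time point and plans no other ECG table.

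**Heart rate.** Under Table 2 footnote e, heart rate is measured at every dialysis, and "if heart rate is clinically significant and outside the prespecified visits per Schedule of Events, the heart rate will be recorded" on the CRF. SAP 9.5.1 says that the "number and percentage of subjects with at least 1 notable value will be tabulated by week and overall".

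**The concern.** The protocol asks for an ET lab sample and ECG so that a patient who stops before Week 12 still has an end-of-treatment value. A window rule suits a dense visit schedule. Here there is one planned post-baseline lab and ECG day, so the rule opens one narrow window at the end of Week 12, and almost every early stopper misses it. The change-from-baseline lab table and the only ECG table would then be silent on most patients who stopped early, including those who stopped for adverse events.

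The heart-rate provision raises a related question. Off-schedule readings are entered because someone judged them clinically significant. Under the priority order they seldom reach a by-visit row, and the SAP leaves open whether they count in the overall row of the notable-value table.

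**Working it through.** The plan gives no figure to reproduce on this point, so the check applies the rule to the visit grid.

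**Inputs**
- Dosing grid: three doses a week for 12 weeks, on Days 7w+1, 7w+3 and 7w+5 for w = 0 to 11. That is 3 x 12 = 36 doses, the last on 7 x 11 + 5 = Day 82. It agrees with the maximum of 36 doses in Protocol 6.1.1.3.
- On-time ET day: the first dialysis after the last dose (Protocol 6.3.1).
- Week 12 visit: SAP 8.2.4.3 says end-of-week measurements "will actually be collected during the first day of the next week", so Week 12 is assessed on Day 85. The window is 85 - 3 = Day 82 to 85 + 1 = Day 86.
- Vital-sign days: 1, 15, 29, 43, 57, 71 and 85 in the protocol (Table 2 footnote e). SAP Table 4 footnote f omits Day 71.

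**Step 1: labs and ECGs.** A patient who stops after any of the first 35 doses (Days 1 to 80) has an on-time ET visit on one of 35 days, from Day 3 to Day 82.

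| Reading of the Week 12 window | Days covered | ET days inside | Share |
|---|---|---|---|
| Day 85, +1/-3 (as written) | 82-86 | 82 | 1/35 = 2.9% |
| Day 85, +/-3 | 82-88 | 82 | 1/35 = 2.9% |
| Day 78 taken as the Week 12 visit, +1/-3 | 75-79 | 75, 78 | 2/35 = 5.7% |

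The result barely depends on how the window is read.

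**Step 2: patients affected.** The documents give no early-termination rate. Assume 5%, 10% or 20% of 350 patients, with ET days spread evenly over the 35.
- 5%: 17.5 ET patients; 17.5 x 34/35 = 17 without a lab or ECG slot and 0.5 with one.
- 10%: 35 ET patients; 35 x 34/35 = 34 without and 1 with.
- 20%: 70 ET patients; 70 x 34/35 = 68 without and 2 with.

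**Step 3: ET vital signs.** On protocol days, each of Days 15, 29, 43, 57 and 71 has three dialysis days within +/-3, and Day 82 reaches Day 85: 5 x 3 + 1 = 16 of 35 ET days (46%). On the SAP days the count is 4 x 3 + 1 = 13 of 35 (37%).

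**Step 4: off-schedule heart rates.** On protocol days, 36 dosing days less the six that are vital-sign days leaves 30. Two off-schedule days sit in each of five windows, plus Day 82: 5 x 2 + 1 = 11 in a post-baseline window. Of the other 19, 18 fall in no window and Day 3 falls only in the Day 1 window. On the SAP days, 36 - 5 = 31 days are off-schedule, 4 x 2 + 1 = 9 are in a post-baseline window and 22 are not. Even inside a window, an unscheduled value is used only if no scheduled or ET value is present.

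**Step 5: summaries not tied to visits.** The SAP 9.4 shift summary uses the highest or lowest class over the treatment period. Protocol 8.8.1 ends that period at the dialysis after the last injection, which is the planned ET day, so an on-time ET lab belongs in it. One uncertainty remains: SAP 9.4 limits lab summaries to subjects with at least one post-baseline time point and does not say whether an unmapped ET sample qualifies.

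**The case against.** The best defence is that labs and ECGs lie outside the window rule. SAP 3.1 speaks of assessments collected by study week, which these are not. Both schedules put End of Treatment and ET in one column, so that column could itself be the time point. This reading is possible, but no lab or ECG analysis text adopts it. SAP Table 4 footnotes d and h name Day 85 without ET. For the Patient Global Impression of Change, SAP 8.2.5.3 does pair Week 12 with end of treatment; labs and ECGs have no such wording. If they do fall outside the rule, the SAP has no rule for ET values, and the same sentence is needed.

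A reader might infer more than the documents support:
- **That unmapped values are discarded.** The SAP never says so. Vital signs and ECGs are listed in full, and on-time ET labs belong in the shift summary.
- **That the vital-sign tables describe completers.** There are five or six post-baseline time points, patients contribute until they stop, and 37-46% of ET days map to one.
- **That a Day 3 reading could become baseline.** Baseline must precede the first dose.
- **That adverse events of special interest are undercounted.** Tachycardia and palpitation are tabulated from adverse-event terms, which use no visit windows.
- **That the safety profile is shown to look cleaner.** The rule applies to both arms, and nothing in the documents fixes the direction of any bias.

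Keeping scheduled values first in by-visit means is sensible, since readings entered only when abnormal would distort them. SAP Section 12 discloses the mapping and priority rules.

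**Conclusion.** The point holds for two outputs. Followed as written, the by-time-point lab change table and the ECG tabulation leave out nearly all ET samples: 1 of 35 possible on-time ET days reaches the Day 85 window, or 2 of 35 on the most lenient reading. Both tables therefore describe mainly patients who reached Day 85.

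The heart-rate part is narrower. On protocol days, 11 of 30 off-schedule dosing days lie in a post-baseline window, and a reading there is used only when no scheduled or ET value exists. Whether the overall notable-value count includes such readings is unstated.

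These counts are of calendar days and assume on-time ET visits on a regular grid. A delayed ET visit, or one following missed doses in Weeks 11 or 12, could land in Days 82-86, so the true mapped share may be higher. The range of 17 to 68 patients rests on the assumed 5-20% early termination, spread evenly. The primary endpoint is unaffected, because SAP 3.1 says it needs no windows.

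**What to change.** Amend SAP 3.1, 9.4 and 9.5 before unblinding:

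1. Tabulate labs and ECGs at a single End of Treatment/Early Termination time point regardless of study day, with a Day 85 completers row alongside.
2. State that lab shifts, clinically important lab values and the overall notable vital-sign count use all post-baseline readings, including ET and unscheduled ones. Say that an ET sample satisfies the requirement for a post-baseline time point. Keep the windows for by-visit means only.
3. Reconcile the Day 71 vital signs, which are in the protocol schedule but absent from SAP Table 4 footnote f.

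The cost is SAP wording and minor programming; no new data are needed. The one drawback is that the combined time point mixes exposure durations, which the completers row makes visible.
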